### **4.6 Interim Analyses**

An interim assessment of blood and scalp PK was performed in the first N=6 patients. For this analysis, the following steps were taken to ensure that unblinded review of PK / PD

parameters did not affect the blinded creation, collection, review or verification of any clinical study data. No PK / PD unblinded reviews were undertaken until all relevant subjects have had all data through Visit 7 verified by source document review and were determined to have all data complete and accurate. Additionally, data from visits through Visit 7 were locked in the EDC system by CRAs, to prevent any changes without permission from the Sponsor. As such, the EDC system audit trail will capture all data activity before and after this Visit 7 lock. All clinical evaluations through Visit 7 for the applicable subjects were done without knowledge of treatment group assignment.

#### **4.7 Sample Size**

Since this is the first multicenter study of ATI-50002 Topical Solution in subjects with stable alopecia universalis and alopecia totalis, sample size considerations were based upon feasibility factors and not on a formal power computation.

#### **4.8 Changes in/ Clarifications to the Conduct of the Study or Planned Analysis**

The Chi-square statistic was not created to compare the incidence of adverse events

Details of analyses of ALADIN scores and immunologic evaluation of blood T-cells will be provided in a separate document.

Scalp biopsy histology will not be analyzed due to limited samples.

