
Endpoints
 
Pharmacokinetic:
 
Concentrations of ATI-50002 in the blood and ATI-50002 in the skin will be measured by a bioanalytical lab using fully validated analytical methods for the blood and qualified methods for the skin.
 
Pharmacodynamic:
		

Change from Baseline in the effects of ATI-50002 induced Janus kinase (JAK) 1/3 inhibition on the ALADIN scores, peribulbar infiltrate and other inflammatory biomarkers.

Safety:

Safety variables to be assessed include: adverse events, clinical laboratory tests (hematology, clinical chemistry, and urinalysis), vital sign measurements (systolic and diastolic blood pressures, respiration rate, heart rate, and oral body temperature), and electrocardiograms.

Efficacy Assessments:

Early signs of vellus hair regrowth are expected to take a minimum of 3 to 6 months in this population. Measurable terminal hair regrowth may take at least 6 months or longer.

Change from baseline in Severity of Alopecia Tool (SALT) score at Week 28 (Visit 13), Week 40 (Visit 14) and Week 52 (Visit 15).

Change from baseline in Alopecia Density and Extent Score (ALODEX) at Week 28 (Visit 13) Week 40 (Visit 14) and Week 52 (Visit 15).

Subject Satisfaction at Week 28 (Visit 13), Week 40 (Visit 14) and Week 52 (Visit 15).

Descriptive summaries of changes from entry into long-term open-label extension in CEA and SEA at Week 28 (Visit 13), Week 40 (Visit 14) and Week 52 (Visit 15) will be performed for those subjects with eyebrow loss.

Study Medication Administration

Double-blind Period: Subjects will apply a minimum of 1.5 mLs up to a maximum of 4 mLs of topical solution to the entire scalp twice-daily as directed.

Open-label Period: Subjects will apply a minimum of 1.5 mLs up to a maximum of 4 mLs of topical solution to the entire scalp twice-daily as directed. In addition, subject may apply a thin film of study medication to the entire affected eyebrow(s) twice-daily for up to 12 months.

Statistical Methods**Sample Size/ Power Calculations**

The planned sample size is 12 subjects.

Statistical Methods**Pharmacokinetic Analyses****Blood Samples**

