5. STUDY OBJECTIVE

5.1.1. Primary Objective

The primary objective is to assess the safety, tolerability, pharmacokinetics and pharmacodynamics of ATI-50002 Topical Solution, 0.46% in subjects with AU or AT.

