12.5.2. Histology

Scalp punch-biopsies will be formalin-fixed and paraffin-embedded and will be sectioned both vertically and horizontally by a qualified dermatopathologist. Specimens will be stained with hematoxylin and eosin (H&E) for “routine” histopathologic evaluation that will include (but is not limited to) diagnosis and evaluation of the presence, quantity, location, and quality of any hair, hair follicles, and inflammatory infiltrate present. Additionally, immunohistochemical (IHC) stains will be employed to identify immune cell populations (e.g., Lymphocytes, cytotoxic T-lymphocytes (CTLs)), and hair-specific keratins. IHC stains to assess inflammatory responses will include but not be limited to, CD8, HLA-DR and ICAM-1. Data will be presented as percent change from baseline in the number of cells/ high power field in regions of interest (peribulbar areas) and in percent change from baseline in the number of cells/mm².

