#### **4.1.4 History of Alopecia**

The type of Alopecia (AT or AU) and prior therapies for alopecia will be summarized by frequency distributions. The time since onset of the current episode of alopecia at entry will be summarized using descriptive statistics (n, mean, standard deviation, median, minimum, and maximum). Summaries will be generated for the AS population. Histological/Cytologic information will be tabulated.

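### SAP 4.8 drops scalp histology, a named pharmacodynamic endpoint under the primary objective, for limited samples, with no counts, no dated decision and no listing

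*SAP*

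**What the plan says.** Protocol Section 5.1.1 states: "The primary objective is to assess the safety, tolerability, pharmacokinetics and pharmacodynamics of ATI-50002 Topical Solution, 0.46% in subjects with AU or AT". The Synopsis defines the pharmacodynamic endpoint as change from baseline in the effects of JAK 1/3 "inhibition on the ALADIN scores, peribulbar infiltrate and other inflammatory biomarkers".

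Protocol Section 12.5.2 describes H&E and immunohistochemistry (CD8, HLA-DR and ICAM-1 among the stains) and fixes the presentation: "Data will be presented as percent change from baseline in the number of cells/ high power field" in the peribulbar regions, and likewise per mm². Sections 7.1, 7.3 and 9.2.1 schedule the pharmacodynamic punch biopsy at Day 1, Day 29 and, for extension subjects, Visit 13.

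SAP Section 4.3 contains no histology analysis. SAP Section 4.8 gives the reason: "Scalp biopsy histology will not be analyzed due to limited samples". The same section sends ALADIN and the blood T-cell evaluation to a separate document. SAP Section 4.1.4, on history of alopecia, says: "Histological/Cytologic information will be tabulated". SAP Section 4.6 reports, in the past tense, an interim assessment of blood and scalp PK in the first 6 patients, with this safeguard: "No PK / PD unblinded reviews were undertaken until all relevant subjects" had their data through Visit 7 verified.

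**The concern.** A named endpoint is removed for a reason that cannot be checked. The SAP does not say whether the problem was biopsies not taken, tissue that could not be read, or too few pairs for a useful summary. Few samples are a good reason to make no inference. They are not a reason to leave existing results out of the report.

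The endpoint carries weight in this design. Protocol Section 9 expects no hair regrowth during the 28-day double-blind period, and Section 4.1 plans no formal SALT or ALODEX comparison between Day 1 and Day 29. Tissue and blood biomarkers are therefore the informative pharmacodynamic evidence from the only vehicle-controlled part of the study. With histology withdrawn and ALADIN and T-cells deferred, this SAP itself specifies no analysis of any tissue or immune biomarker. A reader of the report could not tell whether the histology was favourable, null, unfavourable or never obtained.

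**Working it through.** There is no power calculation or stated biopsy count to reproduce: Protocol 12.1 and SAP 4.7 rest the sample size on feasibility. The check is a count of planned biopsies and a comparison of sections.

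**Planned biopsies.** Inputs: 12 subjects (Protocol 12.1), allocated 2:1 as 8 active and 4 vehicle (Synopsis); one pharmacodynamic biopsy at Day 1 and one at Day 29 for each subject; one more at Visit 13 for each extension subject (Protocol 7.3, 9.2.1).

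- Through Day 29: 12 × 2 = 24, of which 8 × 2 = 16 active and 4 × 2 = 8 vehicle.
- Baseline/Day 29 pairs: 12 (8 active, 4 vehicle).
- Maximum with Visit 13: 24 + 12 = 36, if all 12 enter the extension and have that biopsy.
- In the 6 interim patients, through Visit 7: 6 × 2 = 12, half of the 24.

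These are planned maxima. The SAP gives no number taken or evaluable, so the stated reason cannot be compared with them.

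**How the SAP treats other sparse data.**

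| Data | SAP section | Treatment |
|---|---|---|
| Blood PK, first 6 subjects only | 4.2.1 | Listing only |
| Scalp levels below quantification | 4.2.2, 4.5 | Left out of means, counted separately |
| ALADIN | 4.3.1, 4.8 | Separate document |
| Blood T-cells | 4.8 | Separate document |
| Scalp histology and IHC | 4.8 | Not analysed; no listing, count or other document named |

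Elsewhere, sparse data lead to a listing or a count. Histology is the only one of these with no stated destination.

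**Timing.** SAP 4.6 describes the interim as completed, so the current text was written after it. The interim is described as blood and scalp PK; pharmacodynamics appears only in the wording of the safeguards. Those safeguards protect how clinical data were created, collected, reviewed and verified. They do not address later decisions about what to analyse. No section dates the histology decision or says who knew what when it was made. SAP 4.1.7 still foresees a sponsor review of deviations before unblinding, so full unblinding may not yet have occurred.

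**SAP 4.1.4 against 4.8.** Protocol Appendix 3, the alopecia history form, has no histology or cytology item. The scalp biopsies are thus the only histology source that the protocol describes, and the two SAP sections need to be squared. But 4.1.4 concerns characteristics at entry, not change on treatment.

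**The case against.** The strongest reply is that the change is declared, with a reason, in the SAP section meant for changes. Histology carried no hypothesis test, the study has no power basis, and mechanism is still addressed through ALADIN, whose components include cytotoxic T-lymphocyte infiltration and interferon, and through blood T-cells. This stands as far as it goes: no inferential claim is lost and nothing is concealed. It does not supply the missing counts, date or listing.

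Four further points limit the concern:

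- A reader might infer that the biopsies were wasted. They were not. Protocol 9.2.1 takes each one for histology and RNA sequencing, and 12.5.1 calculates ALADIN on each scalp sample. Only the histology read-out is lost.
- A reader might infer that unblinded results prompted the removal. The documents do not support that. They do not show that histology was read, unblinded or reviewed at the interim, and they do not date the decision.
- A reader might take SAP 4.1.4 as promising the analysis that 4.8 withdraws. It sits among baseline history items and may be leftover wording. It is a loose end rather than a direct contradiction.
- Not analysing is not the same as refusing to list. That is correct: the SAP is silent on a histology listing. But it names listings for other data, such as blood PK and physical examinations, and silence here leaves the endpoint without any specified reporting.

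**Conclusion.** The point holds as a reporting gap that should be closed. A named pharmacodynamic endpoint under the primary objective is withdrawn for limited samples, with no number of samples, no date or blinding status for the decision, and no listing. The selective-reporting risk is unresolved. The text does not justify a finding that selection took place.

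The size is the histology and IHC read-out of up to 24 planned biopsies through Day 29, and at most 36. This assumes 12 subjects randomised with every scheduled biopsy taken and, for the 36, that all enter the extension and reach Visit 13. The actual number is unknown and may be much smaller, particularly as the tissue was shared with RNA sequencing. The conclusion about timing rests only on the past tense of SAP 4.6, because the SAP's date is not in the text available for this review.

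**What to change.** Replace the histology sentence in SAP 4.8 with wording such as: *No summary or inferential analysis of histology will be done; all available histology/IHC results will be listed by subject, arm and visit, with counts of biopsies taken and evaluable per arm and visit.*

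Add one sentence stating when the decision was made and whether those who made it had seen any unblinded data, including any histology. Then reconcile SAP 4.1.4 with 4.8, either by saying which histological information is tabulated and from which specimen, or by deleting the sentence.

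The cost is one listing and one count table, with no new samples and no inference. The listing can cover only results that were actually read. If few or none were, the count table will show that and substantiate the stated reason.

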### **5. STATISTICAL SOFTWARE**

All data summaries and listings will be performed using SAS® Version 9.2 or higher, under Windows operating system.
